## Appendix 2 ELISpot Score Calculation

A single data point for each PBMC sample is obtained **within** the analytical laboratory following the process outlined in the table below.

**Steps 1 – 4 are performed by the analytical laboratory conducting the ELISpot assays. Steps 5 – 8 are performed in a validated SAS program to generate the final data set for statistical analysis by PRA.**

	Step #	Process
Generation of raw data and QC checks performed by Altimmune Analytical Laboratory	1	
ELISpot (ex vivo or cultured) set up to test responses to 9 peptides and LPMIX9.
 
Negative assay controls: no peptide background control.
 
Positive assay controls: stimulation with PHA, a T cell mitogen.
 
N = 3 replicates for each individual peptide, LPMIX9, PHA.
 
N = 6 replicates for no peptide background control.
 
Number of PBMC applied per well: 0.5 - 2 x 10^5 for ex vivo ELISpot, 0.5 – 1% harvested PBMC for cultured ELISpot.

	2	ELISpot raw data output: number of Spot Forming Cells per well (SFC per well)
	3	Quality control #1: visual inspection of wells, values from failed wells excluded and flagged in raw data.
	4	
Quality control #2: positive control PHA threshold: entire sample excluded if PHA fails.
 
PHA threshold for ex vivo ELISpot: mean PHA values > 1500 SFC/10^6 PBMC
 
PHA threshold for cultured ELISpot: mean PHA values for single sample > [mean PHA values for subject's samples across all timepoints] – [2SD PHA values for subject's samples across all timepoints].

Data manipulation performed by Altimmune in SAS validated program	5	
For ex vivo ELISpot, all ELISpot Spot Forming Cells (SFC) will be converted to Spot Forming Cells per million PBMC.
 
(SFC per million PBMC = SFC per well / PBMC per well * 1000000).
 
For cultured ELISpot, all ELISpot SFC will be converted to Spot Forming Cells per million input PBMC.
 
(SFC per million input PBMC = SFC per well / % harvested PBMC applied to well * 100).

	6	For all peptides the mean SFC per million PBMC/input PBMC over the three replicate measurements (wells) will be calculated.
	7	For the negative controls the mean and standard deviation SFC per million PBMC over the six replicate measurements will be calculated.
	8	Ex vivo ELISPOT: for each peptide the ELISPOT score is obtained by:

		
a. first calculating the excess over background
 
excess over background = mean SFC per million PBMC (peptide) – mean SFC per million PBMC (negative control)
 
b. then checking to see if the threshold has been reached: IF (excess over background) < maximum {25 and [2 x SD IFN-<math>\gamma</math> producing cells per million (negative control)]} THEN ELISPOT score = 0; ELSE ELISPOT score = excess over background.
 
Cultured ELISPOT: for each peptide the ELISPOT score is obtained by:
 

a. Applying assay positivity threshold: test antigen SFC/<math>10^6</math> input PBMC reported if > 3SD background SFC/<math>10^6</math> input PBMC.

b. For test antigen responses reported as positive in a., calculate excess over background. = mean SFC per million input PBMC (peptide) – mean SFC per million input PBMC (negative control)

--	--	---

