#### 12.7.1.1 Immune Response

Descriptive statistics (mean, SD, median, quartiles, minimum and maximum) will be generated by treatment group and time point for the following ELISpot score variables:

- ELISpot scores and change from Baseline for individual peptides and LPMIX9
- Sum ELISpot scores and change from baseline across the 9 individual long peptides

Sum ELISpot score is defined as the sum of the 9 ELISPOT scores from the 9 individual peptides.

In addition, standard errors and 95% CIs derived from a one-sample t-test will be presented for change from baseline.

Baseline is defined as the mean of the ELISpot scores prior to the first injection.

In addition, line plots of the mean ( $\pm$  SE) ELISPOT scores over time will be presented by treatment group for each individual peptide, LPMIX9 and the sum score of the 9 individual peptides for the cultured assay over the Immunogenicity Analysis Set. If the Full Analysis differs from the Immunogenicity Analysis Set, then the figures will be repeated for the Full Analysis Set.

Similarly, line plots of each individual patient's ELISPOT score over time will be presented, grouped by treatment group for each individual peptide, LPMIX9 and the sum score of the 9 individual peptides for the cultured assay over the Immunogenicity Analysis Set. If the Full Analysis differs from the Immunogenicity Analysis Set then the figures will be repeated for the Full Analysis Set.

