## 14.0 Allowances for Missing Data

Other than the parameters described in this section, no further imputation for missing data will be performed.

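### The cultured ELISpot rule, as written, tests the un-subtracted count against 3 SD of background and gives failing peptides no score, so null peptides can pass and the nine-peptide sum can lack components

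*SAP*

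**What the plan says.** SAP Appendix 2 (ELISpot Score Calculation), step 8, defines the score differently for the two assays.

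- **Ex vivo.** The excess over the negative control is calculated first. It is then tested: "then checking to see if the threshold has been reached: IF (excess over background) < maximum {25 and [2 x SD" of the negative control. The rule ends "THEN ELISPOT score = 0; ELSE ELISPOT score = excess over background". Every peptide in a valid sample gets a number.
- **Cultured.** Part a reads "Applying assay positivity threshold: test antigen SFC/ 10^6 input PBMC reported if > 3SD background SFC/ 10^6 input PBMC". Part b reads "For test antigen responses reported as positive in a., calculate excess over background". The background mean is not in the threshold, there is no floor, and no value is given to a peptide that fails part a.

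SAP 12.7.1.1 states "Sum ELISpot score is defined as the sum of the 9 ELISPOT scores from the 9 individual peptides", with no rule for a missing component. It defines ELISpot baseline as the mean of the pre-injection scores. SAP 14.0 says that, beyond its listed items, "no further imputation for missing data will be performed". The half-LLOQ rule in SAP 14.1 covers immunogenicity data, but no LLOQ is given for the ELISpot and the rule is not tied to the positivity threshold.

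In SAP Appendix 1 the only ELISpot tables marked Top Line are cultured: 14.2.1.4 (by peptide) and 14.2.1.8 (sum score), both on the Full Analysis Set. All four ELISpot figures are also cultured.

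**The concern.** A positivity threshold should ask whether the peptide wells exceed the background wells by more than noise. Part a of the cultured rule asks whether the peptide count exceeds a multiple of the noise alone. When background is well above zero and its wells agree closely, background itself clears that bar, and a peptide below background can be called positive and receive a negative score.

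The second gap is separate. With no score for failures, the program could use 0, missing, a sum over the peptides that passed, or half an LLOQ. These give different means, and the text does not choose. If failures are left out, per-peptide means and changes from baseline rest on a selected subset that changes from visit to visit.

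The cultured results are the headline immunogenicity output, and SAP 10.2 says the primary analysis is needed to confirm the formulation and dose for the next study.

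**Working it through.** **Inputs from SAP Appendix 2.** Peptides: "N = 3 replicates for each individual peptide, LPMIX9, PHA". Background: "N = 6 replicates for no peptide background control". The conversion to spots per million input PBMC is a multiplication, so it cancels in the threshold comparison if peptide and control wells receive the same share of harvested cells. The plan states no error rate for the rule, so there is no figure to reproduce.

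**Assumptions.** Background level and spread are not in the documents and are varied below. A null peptide has the same true mean as background.

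**1. A single example.** Background wells 18, 20, 22, 19, 21, 20 have mean 20 and SD 1.41. The literal cut-off is 3 × 1.41 = 4.2; background plus 3 SD is 20 + 4.2 = 24.2. A peptide averaging 10 spots, half of background, passes as written and scores 10 − 20 = −10.

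**2. Null pass rate, normal wells.** Let P and B be the peptide and background means, S the background SD (5 df), and CV the background SD divided by its mean.

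- As written: P > 3S is the same as P/(S/√3) > 3√3 = 5.20, a noncentral t with 5 df and noncentrality √3/CV. The pass rate is about 100%, 97%, 85%, 57%, 22% and 3.7% at CV 0.10, 0.20, 0.25, 0.33, 0.50 and 1.0.
- Excess rule: P − B > 3S gives a t with 5 df against 3/√(1/3 + 1/6) = 4.24. The pass rate is 0.4% at any CV.

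Background equals its own 3 SD at CV = 1/3. For Poisson counts CV = 1/√mean, so this is a mean of 9 spots per well.

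**3. Null peptide, Poisson wells (simulated; mean scores in spots per well).**

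| Background per well | 1 | 5 | 10 | 20 | 40 |
|---|---|---|---|---|---|
| Passes, as written | 5% | 30% | 63% | 93% | 99.8% |
| Passes, excess > 3 SD | 1.3% | 0.7% | 0.6% | 0.5% | 0.5% |
| Passes as written with negative score | 0.1% | 6% | 22% | 43% | 49% |
| Mean over passers, as written | 1.2 | 1.1 | 0.7 | 0.2 | 0.0 |
| Mean over passers, excess > 3 SD | 1.6 | 3.6 | 5.1 | 7.1 | 9.9 |
| Mean with failures = 0, as written | 0.07 | 0.32 | 0.44 | 0.20 | 0.01 |
| Mean with failures = 0, excess > 3 SD | 0.02 | 0.03 | 0.03 | 0.04 | 0.05 |

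The true mean is 0 throughout. Dropping failures therefore biases the mean upwards under both readings, and more so under background plus 3 SD.

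**4. The nine-peptide sum, all nine null (Poisson).** As written, at least one peptide fails in 99.7%, 97%, 74%, 10% and 0.1% of samples at 1, 4, 9, 25 and 50 spots. Under background plus 3 SD it is over 99% at every level tried (0.5 to 100 spots). Correcting the threshold alone does not make the sum computable.

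**5. Extra-Poisson spread.** With failures scored 0 under the literal threshold, the null sum is 12.2 at 20 spots and CV 0.4, or 12.2/9 = 1.4 spots per peptide. At 50 spots and CV 0.7 it is 39.9/9 = 4.4, against 9.9/9 = 1.1 under the excess rule. The bound of 0.5 spot in step 3 therefore needs near-Poisson wells.

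**6. Cost of the 3 SD excess cut-off (Poisson).** A true excess of 10 spots over a background of 20 is scored 0 in 68% of cases, and the mean score is 4.1 instead of 10. Over a background of 10, it is scored 0 in 40% of cases, with mean 6.8.

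**7. Units.** With 0.5% to 1% of harvested cells per well, one spot per well is 100/1 = 100 to 100/0.5 = 200 reported units, so 0.44 spot is 44 to 88 units.

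**The case against.** The strongest reply is that the text may not be the operative rule. SAP 12.7.1 presents the algorithm for information only, the scoring runs in a validated program not reproduced in the SAP, and the wording can be laboratory shorthand for 3 SD above background. That reading is possible. It does not close the point: Appendix 2 says steps 5 to 8 generate the data set for analysis, neither document gives another algorithm, and the missing score for failures remains under the shorthand reading, where it matters more (working, steps 3 and 4).

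A reader might infer that most null peptides will be called positive in this trial. The documents do not support that, because they give no background level; at about 1 spot per well the rate is roughly 5%. A reader might also infer that the sum score is always undefined. It lacks a component only when a peptide fails. The two harms also dominate at different backgrounds: false passes when it is high, missing components when it is low. Scoring a non-response 0 would be a derivation rather than imputation, so SAP 14.0 does not forbid it; the gap is that the cultured rule does not say so.

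Three further objections stand. SAP 12.7.1.1 plans no responder rate, so the pass rate is not itself reported; what counts is bias in mean scores. At high background that bias is near zero, and negative scores are what plain subtraction should produce for a null peptide. And a 3 SD excess cut-off attenuates real responses, so it is not free. The ex vivo tables and the separate LPMIX9 score also give evidence that does not rest on the cultured sum.

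**Conclusion.** The cultured rule is wrong as written: it compares an un-subtracted count with 3 SD of background and leaves failures without a score. The missing score is a defect of the text and rests on no assumption. The size of the false-pass problem is conditional: null peptides mostly pass when background CV is below about 1/3 (about 9 spots per well if Poisson), and few pass at very low background.

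If failures are dropped, the null mean over passers is about 0.7 to 1.2 spots per well at backgrounds of 1 to 10 as written, and 1.6 to 9.9 at backgrounds of 1 to 40 under background plus 3 SD. If failures score 0, the null bias per peptide is under 0.5 spot per well with Poisson wells, though it can reach a few spots with strong extra-Poisson spread.

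This should be corrected but does not threaten the trial. The endpoint is secondary and descriptive, SAP 12.0 plans no hypothesis test, and no positivity rate is reported. A reader might infer that the dose choice would be invalidated. The documents do not support that: SAP 10.2 bases it on the primary analysis, which also covers safety and virology.

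**What to change.** Before unblinding:

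1. Write cultured step 8 in the ex vivo form: excess = mean peptide − mean negative control; score = 0 if the excess does not exceed 3 SD of the negative control, otherwise score = excess. Check that the validated SAS program does this.
2. State how the sum score and the baseline mean treat peptides or samples removed by the quality checks in steps 3 and 4. Scoring failures 0 does not cover failed wells or a failed PHA control.
3. Report the untruncated background-subtracted cultured score as a sensitivity summary, because the 3 SD cut-off sets many moderate true responses to 0 when background is high.

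The cost is a few lines of SAP text and code, one extra table, and attenuation of weak and moderate responses in the thresholded score. Item 3 makes that attenuation visible.
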